13.6 Reporting and Exclusions

13.6.1 Evaluation of Toxicity

All patients will be evaluable for toxicity from the time of their first treatment with atezolizumab and/or CYT107.

13.6.2 Evaluation of Response

All patients included in the study must be assessed for response to treatment, even if there are major protocol treatment deviations or if they are ineligible. Each patient will be assigned one of the following categories: (1) complete response, (2) partial response, (3) stable disease, (4) progressive disease, (5) early death from malignant disease, (6) early death from toxicity, (7) early death because of other cause, or (9) unknown (not assessable, insufficient data). [Note: By arbitrary convention, category 9 usually designates the "unknown" status of any type of data in a clinical database.]

All of the patients who met the eligibility criteria (with the possible exception of those who received no study medication) should be included in the main analysis of the

response rate. Patients in response categories 4-9 should be considered to have a treatment failure (disease progression). Thus, an incorrect treatment schedule or drug administration does not result in exclusion from the analysis of the response rate. Precise definitions for categories 4-9 will be protocol specific.

All conclusions should be based on all eligible patients. Subanalyses may then be performed on the basis of a subset of patients, excluding those for whom major protocol deviations have been identified (early death due to other reasons, early discontinuation of treatment, major protocol violations, *etc.*). However, these subanalyses may not serve as the basis for drawing conclusions concerning treatment efficacy, and the reasons for excluding patients from the analysis should be clearly reported. The 95% confidence intervals should also be provided.

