4.4 Patient Enrollment

4.4.1 OPEN

The Oncology Patient Enrollment Network (OPEN) is a web-based registration system available to users on a 24/7 basis. OPEN is integrated with CTSU regulatory and roster data and with the LPOs registration/randomization systems or the Theradex Interactive Web Response System (IWRs) for retrieval of patient registration/randomization assignment. OPEN will populate the patient enrollment data in NCI's clinical data management system, Medidata Rave.

Requirements for OPEN access:

- A valid CTEP-IAM account;
- To perform enrollments or request slot reservations: Must be on an LPO roster, ETCTN corresponding roster, or participating organization roster with the role of Registrar. Registrars must hold a minimum of an Associate Plus (AP) registration type;
- If a Delegation of Tasks Log (DTL) is required for the study, the registrars must hold the OPEN Registrar task on the DTL for the site; and
- Have an approved site registration for the protocol prior to patient enrollment.

To assign an Investigator (IVR) or Non-Physician Investigator (NPIVR) as the treating, crediting, consenting, drug shipment (IVR only), or receiving investigator for a patient transfer in OPEN, the IVR or NPIVR must list the IRB number used on the site's IRB approval on their Form FDA 1572 in RCR. If a DTL is required for the study, the IVR or NPIVR must be assigned the appropriate OPEN-related tasks on the DTL.

Before accessing OPEN, site staff should verify the following:

- Patient has met all eligibility criteria within the protocol stated timeframes; and
- All patients have signed an appropriate consent form and Health Insurance Portability and Accountability Act (HIPAA) authorization form (if applicable).

Note: The OPEN system will provide the site with a printable confirmation of registration and treatment information. Please print this confirmation for your records.

Access OPEN at <https://open.ctsu.org> or from the OPEN link on the CTSU member's website. Further instructional information is on the OPEN section of the CTSU website at

<https://www.ctsu.org> or at <https://open.ctsu.org>. For any additional questions contact the CTSU Help Desk at [name] or [contact].

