12.1 Study Oversight

This protocol is monitored at several levels, as described elsewhere in this section. The Protocol PI is responsible for monitoring the conduct and progress of the clinical trial, including the ongoing review of accrual, patient-specific clinical and laboratory data, and routine and serious AEs; reporting of expedited AEs; and accumulation of reported AEs from other trials testing the same drug(s). The Protocol PI and statistician have access to the data at all times.

All Study Investigators at participating sites who register/enroll patients on a given protocol are responsible for timely submission of data via the mechanism described elsewhere in this section. All studies are also reviewed in accordance with the enrolling institution's data safety monitoring plan.

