12.5 Genomic Data Sharing Plan: N/A

13. STATISTICAL CONSIDERATIONS

This section outlines the statistical analysis strategy and methods for the study. If, after the study has begun, but before the conduct of any analysis, changes are made to primary and/or key secondary hypotheses or the statistical methods related to those hypotheses, then the protocol will be amended (consistent with ICH Guideline E-9). Changes to exploratory or other non- confirmatory analyses made after the protocol has been finalized, along with an explanation as to when and why they occurred, will be listed in the Clinical Study Report (CSR) for the study. Post hoc exploratory analyses will be clearly identified in the CSR. No separate Statistical Analysis Plan (SAP) will be issued for this study.

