13.3 Sample Size/Accrual Rate

During the Safety Run-In phase, 6 patients will be assigned to the experimental arm (atezolizumab + CYT107) with staggered enrollment (refer to [Section 5](#) for details). The AEs will be assessed by the Toxicity Evaluation Committee. If, at any time, 2 or more patients experience a protocol-defined DLT (refer to [Section 5.2](#)), further enrollment into the trial will be suspended.

If the treatment combination of the experimental arm demonstrates an acceptable safety profile in the Safety Run-In (1 or fewer patient experiences a protocol-defined DLT), randomized enrollment into the trial will begin.

A total of 54 patients will be enrolled in this study; 6 patients in the Safety Run-In and 48 patients in the randomized portion of the study. The expected accrual is 4 patients per month total at approximately 8 CITN sites. A study with 48 randomly assigned patients (1:1 randomization) will meet the following statistical parameters: $H_{\text{null}} = 14.8\%$; $H_{\text{alt}} = 45\%$; one-sided alpha of 0.10; power 88%.

The interim futility analysis will be conducted when 24 randomized patients have their first disease assessment and survival information. The futility analysis is based on an O'Brien-Fleming boundary, and the futility boundary will be considered to be crossed when the difference of ORR in the experimental arm – ORR in the control arm is less than -0.0063. Under the null hypothesis, the probability of crossing the futility boundary is 48.2%.

Safety Population: All patients who receive at least 1 dose of the investigational regimen will be considered evaluable for safety and included in the overall safety analysis. For the Safety Run-in phase, in the absence of a DLT, patients must complete the full 28-day DLT window period to be considered evaluable for DLTs. Patients who discontinue from the study before the completion of the full 28-day DLT window for reasons other than the occurrence of a DLT (e.g., withdrawal of consent, rapid tumor progression, death due to rapid tumor progression, AE that does not meet DLT criteria) will not be considered evaluable for DLTs and will be replaced.

Efficacy Population: The efficacy analysis will be conducted on all randomized patients, based upon the intent-to-treat population.

PLANNED ENROLLMENT REPORT

Racial Categories	Ethnic Categories		Totals
	Not Hispanic or Latino	Hispanic or Latino	

	Female	Male	Female	Male	
American Indian/ Alaska Native	1	2			3

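### Section 13.6.2 bases the main response-rate analysis and all conclusions on eligible patients, while section 13.3 says all randomized patients, and nothing says which prevails

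*Combined protocol and SAP*

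**What the plan says.** Section 13.3, under its efficacy population heading, states: "The efficacy analysis will be conducted on all randomized patients, based upon the intent-to-treat population".

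Section 13.6.2 says something else about the same endpoint:

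- Every patient must be assessed for response, "even if there are major protocol treatment deviations or if they are ineligible". This sentence concerns assessment.
- The main response-rate analysis should include patients who met the eligibility criteria, "with the possible exception of those who received no study medication".
- "All conclusions should be based on all eligible patients". Subset analyses that leave out patients with major deviations may not support efficacy conclusions.
- Response categories 4 to 9, which include early death and unknown response, count as treatment failures.

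Section 11.1.1 adds a third, narrower group evaluable for objective response: measurable disease at baseline, at least one cycle of therapy, and disease re-evaluated (or progression before the end of cycle 1).

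Section 13 closes off any later clarification in another document: "No separate Statistical Analysis Plan (SAP) will be issued for this study".

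Other relevant text: the trial is open-label (2.1). Randomization may come up to 5 business days before treatment starts (5). The registration of a patient who receives no protocol therapy may be canceled (4.5). On data access, "The Protocol PI and statistician have access to the data at all times" (12.1). Before opening the enrollment system, site staff should verify: "Patient has met all eligibility criteria within the protocol stated timeframes" (4.4.1).

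**The concern.** Sections 13.3 and 13.6.2 govern the same primary test and give different denominators. A randomized patient later found ineligible is in under 13.3 and outside the set that 13.6.2 names. A randomized patient who is never dosed is in under 13.3 and undecided under 13.6.2.

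The choice could be made late and with knowledge of the data. Treatment arm is known to everyone, and the investigator and statistician see the data throughout. An untreated patient could be removed once the arm is known; an ineligible patient could be removed once arm and response are both known. The direction of any bias cannot be predicted. An untreated patient is a failure under intention to treat, whereas an ineligible patient has been assessed and may be a responder or a non-responder.

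With 24 patients per arm, one exclusion can decide a close result.

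**Working it through.** **Inputs.** 48 randomized 1:1, so 24 per arm; ORR 14.8% vs 45%; one-sided alpha 0.10; power 88%; futility if the ORR difference is below -0.0063 (13.3). The primary test is Cochran-Mantel-Haenszel (CMH) (13.2.1), and randomization is unstratified (13.4).

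**The plan's own figures.** The unpooled two-proportion formula gives:

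Power = Φ[(0.45 − 0.148)/√(0.148×0.852/24 + 0.45×0.55/24) − 1.2816] = Φ(2.4205 − 1.2816) = 87.3%, against the stated 88%.

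Exact enumeration of the single-stratum CMH test gives 85.6%. For futility, assuming 12 per arm at the interim, Φ[−0.0063/√(2×0.148×0.852/12)] = 48.3%, against the stated 48.2%. Both design figures therefore use every randomized patient, with no allowance for exclusions.

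**Effect of one exclusion on the final test.** With x1 of n1 experimental and x0 of n0 control responders, m = x1 + x0 and N = n1 + n0:

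z = (x1 − n1·m/N) / √[n1·n0·m·(N−m) / (N²(N−1))], one-sided p = 1 − Φ(z), success if z ≥ 1.2816.

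Example: 9/24 vs 5/24 has expected count 24×14/48 = 7 and variance 24×24×14×34/(48²×47) = 2.532, so z = 2/1.591 = 1.257 and p = 0.1044. With one experimental non-responder dropped (9/23 vs 5/24), z = 1.357 and p = 0.0875.

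| Dropped patient | All randomized (exp. vs control) | p | After exclusion | p |
|---|---|---|---|---|
| Experimental non-responder | 9/24 vs 5/24 | 0.1044, fail | 9/23 vs 5/24 | 0.0875, success |
| Control non-responder | 8/24 vs 4/24 | 0.0935, success | 8/24 vs 4/23 | 0.1076, fail |
| Control responder (ineligible) | 7/24 vs 4/24 | 0.1540, fail | 7/24 vs 3/23 | 0.0908, success |
| Experimental responder (ineligible) | 7/24 vs 3/24 | 0.0798, success | 6/23 vs 3/24 | 0.1209, fail |

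**How common such cases are.** These tables were chosen near the boundary. Exact enumeration at 24 per arm gives:

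| True ORR (exp. vs control) | Some single exclusion would flip the decision | One random experimental patient dropped | One random control patient dropped |
|---|---|---|---|
| 14.8% vs 14.8% | 17% | 1.1% | 1.3% |
| 45% vs 14.8% | 9% | 3.3% | 2.7% |
| 30% vs 14.8% (assumed) | 24% | 4.6% | 4.7% |

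The second column measures fragility and is not the probability that a flip occurs.

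**Type I error and power.** Model untreated patients as certain failures and ignore the interim look. Excluding them, with 0 to 4 per arm in the combinations run, leaves type I error between 9.2% and 11.4% (10.2% with none). With 2 per arm, power is 83.0% whether they are excluded or kept as failures. With 4 per arm, it is 81.8% excluded and 80.0% kept. With none it is 85.6%. Selective removal of ineligible patients was not modelled, because the documents give no basis for a rate.

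**Interim look.** Assume 12 per arm. A tie of k responders per arm has difference 0 and does not cross -0.0063. Dropping one control non-responder gives k/12 − k/11 = −k/132, which is −0.0076 for k = 1 and −0.0152 for k = 2; both cross. Ties with at least one responder per arm have probability 21.1% at 14.8% in both arms and 4.4% at 45% vs 14.8%. These are the chances of being at that edge, not error rates.

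**The case against.** The best defense is that 13.6.2 is generic text. It says the definitions of categories 4 to 9 will be protocol specific, its numbering skips category 8, and it speaks in terms of what should be done. Section 13.3 is declarative and written for this trial. The sentence on the main analysis can be read as a rule about whom to include, without barring anyone, and the sentence on conclusions as a bar on subset-based claims. That reading is reasonable for the first sentence but not for the second, which names eligible patients as the basis for every conclusion. Section 13.3 is the more trial-specific text, but nothing says that it overrides.

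It is also fair to say that the route to bias is conditional. Eligibility is a baseline property and is checked before enrollment. Harm needs ineligibility to be discovered or judged late, and differently by arm or outcome. No section describes an eligibility review after randomization, and 4.5 does not say that a canceled registration leaves the efficacy analysis. Counting categories 4 to 9 as failures closes the more usual route of dropping unassessed patients. The random-exclusion flip rates are low. All of this limits the likely size of the problem but leaves the contradiction in place.

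Finally, 13.6.2 does not mention the interim analysis, and 13.3 triggers it on 24 randomized patients. The interim point is therefore a request for clarity and not a second contradiction.

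**Conclusion.** The concern holds. The plan is wrong as written: it gives two incompatible analysis sets for the primary endpoint, and one of them allows exclusions after randomization in an open-label trial. Confidence is high for the contradiction, which can be read directly from the two sections. The size of its effect is unknown, because no ineligibility or non-treatment rate is given. The worked tables show only that one patient can reverse a close decision in either direction, assuming 24 per arm and the uncorrected CMH test. The case for intention to treat here is a single pre-specified set protected by randomization. It is not a power case, and no type I error inflation is claimed. This should be fixed before any analysis.

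A separate point on secondary endpoints: 11.1.6 times PFS from start of treatment, so a randomized but untreated patient has no PFS start date, and OS has no stated origin. The verdict above does not depend on this.

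**What to change.** - Rewrite 13.6.2 so that the main ORR analysis and all conclusions use all randomized patients, as randomized, in line with 13.3. Keep categories 4 to 9 as failures.
- Delete the possible exception for patients who received no study medication.
- Label the eligible-only analysis and the response-evaluable analysis of 11.1.1 as supportive.
- State in 13.3 that the interim futility comparison excludes no randomized patient for ineligibility.
- State in 4.5 that canceling a registration does not remove a randomized patient from the efficacy analysis.
- Separately, time PFS (11.1.6) and OS from randomization in the randomized comparison. The run-in patients, who are not randomized, can keep start of treatment as their origin.

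The cost is wording in 13.6.2, 13.3, 4.5 and 11.1.6 through a protocol amendment, for which section 13 already provides before any analysis. No new patients or data are needed. The reported ORR may shift slightly in either direction compared with an eligible-only analysis.

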APPENDIX A PERFORMANCE STATUS CRITERIA

ECOG Performance Status Scale		Karnofsky Performance Scale	
Grade	Descriptions	Percent	Description
0	Normal activity. Fully active, able to carry on all pre-disease performance without restriction.	100	Normal, no complaints, no evidence of disease.
		90	Able to carry on normal activity; minor signs or symptoms of disease.
1	Symptoms, but ambulatory. Restricted in physically strenuous activity, but ambulatory and able to carry out work of a light or sedentary nature (e.g., light housework, office work).	80	Normal activity with effort; some signs or symptoms of disease.
		70	Cares for self, unable to carry on normal activity or to do active work.
2	In bed <50% of the time. Ambulatory and capable of all self-care, but unable to carry out any work activities. Up and about more than 50% of waking hours.	60	Requires occasional assistance but is able to care for most of his/her needs.
		50	Requires considerable assistance and frequent medical care.
3	In bed >50% of the time. Capable of only limited self-care, confined to bed or chair more than 50% of waking hours.	40	Disabled, requires special care and assistance.
		30	Severely disabled, hospitalization indicated. Death not imminent.
4	100% bedridden. Completely disabled. Cannot carry on any self-care. Totally confined to bed or chair.	20	Very sick, hospitalization indicated. Death not imminent.
		10	Moribund, fatal processes progressing rapidly.
5	Dead.	0	Dead.

APPENDIX B CTEP MULTICENTER GUIDELINES

If an institution wishes to collaborate with other participating institutions in performing a CTEP-sponsored research protocol, then the guidelines below must be followed.

Responsibility of the Protocol Chair

- The Protocol Chair will be the single liaison with the CTEP Protocol and Information Office (PIO). The Protocol Chair is responsible for the coordination, development, submission, and approval of the protocol as well as its subsequent amendments. The protocol must not be rewritten or modified by anyone other than the Protocol Chair. There will be only one version of the protocol, and each participating institution will use that document. The Protocol Chair is responsible for assuring that all participating institutions are using the correct version of the protocol.
- The Protocol Chair is responsible for the overall conduct of the study at all participating institutions and for monitoring its progress. All reporting requirements to CTEP are the responsibility of the Protocol Chair.
- The Protocol Chair is responsible for the timely review of AE to ensure safety of the patients.
- The Protocol Chair will be responsible for the review of and timely submission of data for study analysis.

Responsibilities of the Coordinating Center

- Each participating institution will have an appropriate assurance on file with the Office for Human Research Protection (OHRP), NIH. The Coordinating Center is responsible for assuring that each participating institution has an OHRP assurance and must maintain copies of IRB approvals from each participating site.
- Before the activation of the protocol at each participating institution, an OHRP form 310 (documentation of IRB approval) must be submitted to the CTEP PIO.
- The Coordinating Center is responsible for central patient registration. The Coordinating Center is responsible for ensuring that IRB approval has been obtained at each participating site before the first patient registration from that site.
- The Coordinating Center is responsible for the preparation of all submitted data for review by the Protocol Chair.
- The Coordinating Center will maintain documentation of AE reports. There are 2 options for AE reporting: (1) participating institutions may report directly to CTEP with a copy to the Coordinating Center, or (2) participating institutions report to the Coordinating Center who in turn report to CTEP. The Coordinating Center will submit AE reports to the Protocol Chair for timely review.
- Audits may be accomplished in one of 2 ways: (1) source documents and research records for selected patients are brought from participating sites to the Coordinating Center for audit, or (2) selected patient records may be audited on-site at participating sites. If the NCI chooses to have an audit at the Coordinating Center, then the Coordinating Center is responsible for having all source documents, research records, all IRB approval documents, NCI Drug Accountability Record forms, patient registration lists, response assessments scans, x-rays, etc., available for the audit.

Inclusion of Multicenter Guidelines in the Protocol

- The protocol must include the following minimum information:
 - The title page must include the name and address of each participating institution and the name, telephone number, and email address of the responsible investigator at each participating institution.
 - The Coordinating Center must be designated on the title page.
 - Central registration of patients is required. The procedures for registration must be stated in the protocol.
 - Data collection forms should be of a common format. Sample forms should be submitted with the protocol. The frequency and timing of data submission forms to the Coordinating Center should be stated.
 - Describe how AEs will be reported from the participating institutions, either directly to CTEP or through the Coordinating Center.
 - Describe how Safety Reports and Action Letters from CTEP will be distributed to participating institutions.

Agent Ordering

- Except in very unusual circumstances, each participating institution will order DCTD-supplied investigational agents directly from CTEP. Investigational agents may be ordered by a participating site only after the initial IRB approval for the site has been forwarded by the Coordinating Center to the CTEP PIO.

Step 6. Derive the overall response using the table below.

Overall Response	Criterion
irCR	Complete disappearance of all lesions (whether measurable or not, and no new lesions) confirmed by a repeat, consecutive assessment ≥ 4 weeks from the date first documented
irPR	Decrease in tumor burden $\geq 50\%$ relative to baseline confirmed by a consecutive assessment ≥ 4 weeks from the date first documented
irSD	Criteria for irCR, irPR, and irPD are not met; does not require confirmation
irPD	Increase in tumor burden $\geq 25\%$ relative to nadir confirmed by a consecutive assessment ≥ 4 weeks from the date first documented

irCR = immune-related complete response; irPD = immune-related progressive disease; irPR = immune-related partial response; irSD = immune-related stable disease.

Determination of irBOR

Once a patient has completed all tumor assessments, his/her irBOR may be determined:

Condition	irBOR
At least one irCR	irCR
At least one irPR and no irCR	irPR
At least one irSD and no irCR and no irPR	irSD
At least one irPD and no irCR, no irPR, and no irSD	irPD

irBOR = immune-related best overall response; irCR = immune-related complete response; irPD = immune-related progressive disease; irPR = immune-related partial response; irSD = immune-related stable disease.

